9.2.2 Serious Adverse Event Definition

An SAE is any untoward medical occurrence that at any dose:

• Results in death

- Is life-threatening (an event which places the patient at immediate risk of death from the event as it occurred. It does not include an event that had it occurred in a more severe form might have caused death)
- Requires inpatient hospitalization or prolongation of existing hospitalization
- Results in persistent or significant disability or incapacity
- Is a congenital abnormality or birth defect
- An important medical event that may not be immediately life-threatening or result in death or hospitalization but may jeopardize the patient and may require intervention to prevent one of the other outcomes listed in the definition above (eg, events include allergic bronchospasm requiring intensive treatment in an emergency room or at home, blood dyscrasias, convulsions, or the development of drug dependency or abuse).

9.2.3 Eliciting Adverse Event Information

The patient should be asked about medically relevant changes in his health since the last visit. The patient should also be asked if he has been hospitalized, had any accidents, used any new medications, or changed concomitant medication routines (both prescription and over-the-counter).

In addition to patient observations, AEs will be documented from any clinically relevant laboratory findings, physical examination findings, ECG changes, or other findings that are relevant to patient safety.

9.2.4 Adverse Event Reporting

The Investigator is responsible for reporting all AEs that are observed or reported from the first administration of study drug in this study, regardless of their relationship to study drug, through the follow-up visit.

All AEs must be fully recorded in the source records for the clinical study center and in the eCRF for the patient, whether or not they are considered to be drug related. Each AE must be described in detail: onset time and date, description of event, severity, relationship to investigational product, action taken, and outcome (including time and date of resolution, if applicable).

9.2.5 Assessment of Causality

Causal relationship assessment to drug treatments is required for purposes of reporting AEs. To promote consistency, the following guidelines should be taken into consideration along with good clinical and scientific judgment when determining the relationship of drug treatments to an AE:

Definitely Related: A clinical event, including laboratory test abnormality, occurring in a

plausible time relationship to the medication administration, and which cannot be explained by concurrent disease or other drugs or chemicals. The response to withdrawal of the drug should be clinically plausible.

Possibly Related: A clinical event, including laboratory test abnormality, with a

reasonable time sequence to the medication administration, but which could also be explained by concurrent disease or other drugs or chemicals. Information on the drug withdrawal may be lacking or

unclear.

Unlikely Related: A clinical event, including laboratory test abnormality, with little or no

temporal relationship to medication administration, and which other drugs, chemicals, or underlying disease provide plausible explanations.

Not Related: A clinical event, including laboratory test abnormality that has no

temporal relationship to the medication or has more likely alternative

etiology.

9.2.6 Assessment of Severity

Adverse events are to be graded according to the categories detailed below:

Mild: Mild events are those which are easily tolerated with no disruption of

normal daily activity.

Moderate: Moderate events are those which cause sufficient discomfort to

interfere with normal daily activities.

Severe: Severe events are those which incapacitate and prevent usual activity.

Changes in severity should be documented in the medical record to allow assessment of the duration of the event at each level of severity. Adverse events characterized as intermittent require documentation of the start and stop of each incidence. When changes in the severity of an AE occur more frequently than once a day, the maximum severity for the experience that day should be noted. If the severity category changes over a number of days, then those changes should be recorded separately (with distinct onset dates).

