10.2.6 Safety Analyses

Adverse events will be summarized by the MedDRA System Organ Class and Preferred Term. Incidence of treatment-emergent adverse events (TEAEs; those events that started after exposure to study drug or worsened in severity after dosing) will be presented by dose level and overall. Incidence of TEAEs will also be presented by maximum severity and relationship to study medication or underlying hemophilia. The incidence of SAEs and AEs leading to discontinuation of treatment will also be tabulated. By-patient listings will be provided for deaths, SAEs, and events leading to discontinuation of treatment.

Descriptive statistics will be provided for clinical laboratory data (including biochemistry, hematology, urinalysis, and coagulation) and vital signs data, presented as both actual values and changes from baseline relative to each on-study evaluation. Laboratory shift tables from baseline to worst values will be presented. Baseline will be defined as the last observation on or before Day 1. Abnormal physical examination findings, 12-lead ECG data, and antidrug antibody results will be presented in a by-patient data listing. Antidrug antibody results will also be tabulated.

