5.2 GENERAL METHODS

Both efficacy and safety analysis under the original and revised dose regimens will be analyzed separately, unless otherwise specified. The data collected during the 2020 voluntary dose pause will be analyzed along with the pre-pause data.

A significant dose is defined as any single dose of fitusiran that is greater than or equal to 20 mg. Before the voluntary dose pause, the analysis period for efficacy endpoints starts from the date of first significant dose up to the earlier of 2020 voluntary dose pause date or the last day of study follow-up. For safety endpoints, the analysis will be performed based on LTE14762 study period data only up until the dose restart date. Date of first significant dose in the TDR14767(ALN-AT3SC-001) and LTE14762 study/studies will be designated as Treatment Day 1; there will be no Treatment Day 0. Participants who receive doses (either weight-dependent or weight-independent) of at least 20 mg but less than 75 mg will be “classified” as “50 mg” participants, while participants receiving doses of greater than or equal to 75 mg will be “classified” as “80 mg” participants (except PK analysis in which actual dose on Day of PK sample collection will be used). However, for purposes of efficacy and safety analyses and summaries in the final CSR report for the LTE14762 study, the classification of each participant under the original dose and regimen will be according to the fixed dose to which they are eventually taken by the end of the LTE14762 study original dose period. For example, participants who received a 50 mg dose in TDR14767(ALN-AT3SC-001) or LTE14762 and then were switched to 80 mg dose at some point in time during the LTE14762 study, are classified in the LTE14762 study as “80 mg” participants (except for PK analyses). Treatment after the volunteer dose pause will be treated as each participant’s treatment sequence.

[figure not shown]
Treatment Days under the original dose and regimen will be calculated as evaluation date – first significant dose date +1 and pre-treatment days will be calculated as evaluation date – first significant dose date. (The pre-treatment day formula applies when evaluation date < first significant dose date; ie, for example, there will be pre-treatment Days ... -3, -2, -1, then treatment Day 1, 2, 3, 4, ...; there is no “pre-Treatment Day 0” nor is there any “Treatment Day 0”).

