We also define Study Days in the LTE14762 study as the number of days from first significant dose in LTE14762 and calculate similarly as the Treatment Days. For participants who received first significant dose in LTE14762, the Study Days is the same as the Treatment Days.

For participants under the revised dose and regimen, both efficacy and safety data will be analyzed from the dose re-start Day 1 up until the last day of study follow-up.

Treatment day after the dose re-start will be calculated as evaluation date – first dose date after dose re-start + 1 (days). It should be not applicable for assessments before the dose re-start. A summary of study periods and start day in analysis is outlined in [Figure 1](#)

Figure 1 Study periods and analysis start day summary

	Original dose and regimen	2017 clinical hold/2020 voluntary dose pause	Revised dose and regimen
Efficacy analysis	Starts from first significant dose of fitusiran in TDR14767(ALN-AT3SC-001) or LTE14762 and in terms of treatment days.	Starts from the 29th days after last dose date before the hold/pause	Starts from first dose date of revised dose and regimen and in terms of treatment days
Safety analysis	Starts from first significant dose of fitusiran in LTE14762 and in terms of study days	Starts from the day after last dose date before the hold/pause and in terms of study days	Starts from first dose date of revised dose and regimen and in terms of study days

Summary statistics will be reported by analysis visits defined in [Section 5.10](#) below. Unless otherwise noted, tables under both the original and revised dose regimens will be presented by hemophilia type, inhibitor type and overall. Participants who received a significant dose in TDR14767(ALN-AT3SC-001) will be considered as a subgroup in the analysis under the original dose and regimen. Details will be specified in the [Section 6.11](#).

Categorical data summary will include the number and percentage of participants within each category, with a category for missing data. Continuous data summary will include descriptive statistics - the number of participants, mean, median, standard deviation (SD), first quartile (Q1), third quartile (Q3), minimum, and maximum. The precision of the measurement for each continuous variable will be used to determine the number of decimal places to present in tables, figures and derived listings. Minimum and maximum values will be reported with the same

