6.8.2 Adverse events

Adverse events (AE) analysis will include treatment-emergent events, with onset occurring in the LTE14762 study. (Note: All AEs collected in LTE14762 are considered TEAE because all participants received dose in TDR14767(ALN-AT3SC-001).)

All AEs will be coded using the MedDRA(version 25.1 or later) coding system and displayed in tables and data listings using system organ class (SOC) and preferred term (PT). AEs will be summarized by the numbers and percentages of participants reporting at least 1 AE, having at least 1 AE by primary SOC and PT. A participant with multiple occurrences of an AE will be counted only once in the respective AE category. Participants who report multiple occurrences of the same AE (preferred term) will be classified according to the most related or most severe occurrence, respectively.

All AE summaries will be summarized (frequency counts and percentages) by system organ class and/or preferred term, unless specified otherwise. The SOC will be presented according to

international standards (MedDRA Internationally Agreed Order), and the preferred term will be sorted within each SOC in decreasing order of frequency.

The following events are considered to be AEs of special interest (AESI):

1. ALT or AST elevations $>3 \times$ ULN
2. Suspected or confirmed thromboembolic events
3. Severe or serious injection site reactions (ISRs), ISRs that are associated with a recall phenomenon (reaction at the site of a prior injection with subsequent injections) or, those that lead to temporary dose interruption or permanent discontinuation of study drug.
4. Systemic (injection associated reactions (IARs), defined as hypersensitivity reactions which are related or possibly related to IMP.
5. Cholecystitis
6. Cholelithiasis

The identification of cholecystitis and cholelithiasis will be a combination of systematic search of higher level group term (HLGT) and AESI collected as it is in CRF. AEs whose HLT fall into the categories listed below will be considered as AESI of cholecystitis and cholelithiasis:

1. Bile duct disorders,
2. Gallbladder disorders
3. Hepatic and hepatobiliary disorders

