An overall summary of TEAEs will include the number and percentage of participants with any TEAE, any TEAE assessed by the Investigator as related to study drug (possibly related or definitely related), any serious TEAE (TESAE), any TESAE related to study drug, any TEAE of special interest; any AE/SAE leading to permanent study drug discontinuation, any TEAE/TESAE leading to study withdrawal, and any deaths. The TEAE onset within any major surgery period will be provided in a separate column in the overview summary statistics as well as in the overall column. They will be excluded from the rest of by-indication columns in the table.

Tabulations of TEAEs by SOC and PT excluding those AE onsets within major surgery period will be produced for the following:

1. TEAEs
2. TEAEs by severity
3. Treatment emergent SAEs
4. TEAEs related to study drug
5. Treatment emergent SAEs related to study drug
6. TEAEs leading to permanent study drug discontinuation
7. Treatment emergent SAEs leading to permanent study drug discontinuation
8. TEAEs leading to study withdrawal
9. Treatment emergent SAEs leading to study withdrawal
10. Treatment emergent AESI (Adverse Events of Special Interest)
11. TEAEs potentially consistent with Covid-19. These AEs will be identified based on SMQ group searching.

All AEs will be listed along with the information collected on those AEs, eg, AE relationship to study drug, AE outcome etc. By-participant listings will also be provided for the following: all participant deaths, all SAEs, and all AEs leading to permanent study drug discontinuation or study withdrawal, all AEs leading to death. AE onset during the major surgery period will also be included in each of the by-participant listing with major surgery flag.

The incidence rate of severe or serious ISRs will also be summarized. The incidence rate is defined as the number of severe or serious ISRs per study drug injection. If multiple ISRs occur between two consecutive injections, they will be counted under the first injection as 1 ISR.

Because of hepatitis C infected participant got enrolled in the TDR14767(ALN-AT3SC-001) study, participants with treatment emergent ALT or AST elevations > 3 ULN AESI will be analyzed based on their HCV status at the enrollment of LTE14762 study.

Additional summary of incidence rate for TEAE, SAE, AEs leading to permanent study drug discontinuation and AESI before and after the 2020 dose pause by primary SOC and PT will be provided.

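### An adverse event that is ongoing at the 2020-pause restart and only becomes milder afterwards can be counted again as a revised-regimen TEAE, because nothing links its severity records across the restart

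*Protocol*

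**What the plan says.** **Recording.** Protocol 9.2.6 sets the rule for AEs whose severity changes: "If the severity category changes over a number of days, then those changes should be recorded separately (with distinct onset dates". It does not distinguish worsening from improvement. Changes within a single day are reduced to that day's maximum, so the rule concerns changes across days. Protocol 9.2.4 requires each AE to be entered in the eCRF with its onset and severity.

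**Treatment emergence.** Protocol 10.2.6 defines TEAEs as "those events that started after exposure to study drug or worsened in severity after dosing". SAP 6.8.2 states: "Adverse events (AE) analysis will include treatment-emergent events, with onset occurring in the LTE14762 study". It then notes: "All AEs collected in LTE14762 are considered TEAE because all participants received dose in TDR14767(ALN-AT3SC-001".

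**Split at restart.** For the original regimen, SAP 5.2 says: "For safety endpoints, the analysis will be performed based on LTE14762 study period data only up until the dose restart date". Data from the pause itself are analysed with the pre-pause data. For the other side: "For participants under the revised dose and regimen, both efficacy and safety data will be analyzed from the dose re-start Day 1". SAP 6.8 confirms that the two regimens are analysed separately.

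**Output.** SAP 6.8.2 plans an "Additional summary of incidence rate for TEAE, SAE, AEs leading to permanent study drug discontinuation and AESI before and after the 2020 dose pause", by system organ class and preferred term.

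**Nearest safeguards.** SAP 6.8.2 counts a participant once per AE category, at the most severe or most related occurrence. SAP 5.5 and 6.8 add a baseline at restart, but only for laboratory, vital sign and ECG summaries.

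**The concern.** The separate-record rule is reasonable for describing the course of one event. The difficulty comes when the data are cut at a date and each side is counted by onset. An AE that began under the original regimen or during the pause, and that steps down a severity grade after restart, leaves a record whose onset lies in the revised-regimen window. The SAP makes every LTE14762 AE treatment-emergent because all participants were dosed in the parent study. That settles emergence at entry to the extension. It does not ask whether an event is emergent under the revised regimen.

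Long-term safety is the primary objective, and the revised regimen was introduced to mitigate thrombotic risk. The before/after-pause summary is where a reader will look for the effect of that change. An improving old event should not appear there as a new event under the revised regimen.

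**Working it through.** The documents state no figure on this point, so there is nothing to reproduce. The check applies the written rules to constructed records and then sizes one miscount.

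**Step 1: apply the rules.** Set restart at day 0 and take three constructed events:

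| Event | Record before restart | Record after restart | What happened |
|---|---|---|---|
| A | moderate, day −200 | mild, day +20 | improved only |
| B | mild, day −150 | moderate, day +30 | worsened |
| C | none | mild, day +40 | new |

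Counts in each window:

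- Original regimen, SAP rule (record onset before restart): A and B, so 2.
- Revised regimen, SAP rule (record onset on or after restart): A, B and C, so 3.
- Revised regimen, test of started or worsened since restart: B and C, so 2.

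The difference is event A, the one that only improved. It appears in both regimen columns.

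**Step 2: look for a rule that removes it.**

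- The once-per-participant rule works inside one category of one table. It does not connect a record in the original-regimen table to one in the revised-regimen table.
- The restart baseline does not extend to AE severity.
- The only explicit collapsing rule in SAP 6.8.2 is for severe or serious injection site reactions between two consecutive injections.

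**Step 3: direction for participant counts.** Event A belongs in the original-regimen column under either rule, so that column is unchanged. An event that starts after restart cannot acquire an onset before it. The miscount can therefore only add to the revised-regimen column.

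**Step 4: size per affected participant and row.** The increment is 100/N percentage points, where N is the size of Safety analysis set 2. The documents do not give N, so a range is assumed. The top value is the planned maximum enrolment. The value 34 equals the 13 + 21 participants reported in Protocol 1.3.3 for August 2017.

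| Assumed N | 100/N (points) |
|---|---|
| 48 | 2.1 |
| 34 | 2.9 |
| 25 | 4.0 |
| 20 | 5.0 |
| 15 | 6.7 |

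The increment is zero if the participant already has a genuine post-restart event in that row.

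**Step 5: record-based rates.** SAP 6.8.2 does not define the general incidence rate. If it counts records, an event passing from severe to moderate to mild contributes three instead of one. That can happen in either period, so both rates inflate and the net direction is not determined.

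**The case against.** **The recording premise is partly inferred.** Protocol 9.2.6 opens by speaking of the medical record and of how long an event lasts at each severity level. How a change is keyed is an eCRF matter, and the eCRF completion guidelines are not available here. The SAP also never says in one sentence that an AE goes to a regimen by the onset date of its record. This stands as a limit. But the protocol asks for distinct onset dates and requires onset and severity in the eCRF, and the SAP selects AEs by onset and splits safety data at the restart. No text points to another allocation. If the eCRF keeps one entry with one onset, the problem does not arise, and the SAP could say so.

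**A reader might infer that the SAP departs from the protocol's TEAE definition.** It does not. The first limb of Protocol 10.2.6, onset after exposure, is met by every AE starting in LTE14762, so restoring the second limb would not remove a step-down record. The gap is the lack of an emergence test at restart.

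**A reader might infer that thrombosis and liver AESIs are hit hardest.** The documents do not support that. Severity is graded by effect on daily activity, whereas the ALT/AST AESI is a laboratory threshold, so a falling ALT need not change the grade. An event that began before the last pre-pause dose must also outlast the pause. SAP Table 4 puts that between 31 October 2020 and 26 January 2021, at least 87 days (30 + 31 + 26).

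**The consequence is limited.** The summary is descriptive and additional, and all AEs are listed by participant, so a carried-over event could be found by hand. That is true, but it leaves the tabulated figure wrong.

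**Conclusion.** The point holds. Read literally, the plan counts an LTE14762 AE that is ongoing at restart and later only decreases in severity under both regimens. In participant-level tables the error can only raise the revised-regimen column, by 1/N per affected participant and row: 2.1 to 6.7 percentage points for an assumed N of 48 to 15.

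This rests on multi-day severity changes being keyed as separate entries and on allocation by record onset, which is inferred from SAP 5.2, 6.8 and 6.8.2. The number of participants affected cannot be derived and may be small or zero. Parent-study AEs still ongoing are medical history and are not affected unless they deteriorate. A general claim that the error always runs against the revised regimen would go too far, because record-based rates inflate in both periods.

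**What to change.** Add one paragraph to SAP 6.8.2:

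- Consecutive records of the same AE that differ only in severity are linked into one event, which keeps its first onset date.
- An event with first onset before restart is counted in the original-regimen tables at its maximum severity before restart.
- An event is treatment-emergent under the revised regimen only if it first starts on or after restart Day 1, or if its severity after restart exceeds its severity at restart. It is then reported there at its maximum post-restart severity.
- The before/after-pause incidence summary uses linked events, not records.

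Severity must be kept separate by period. Giving a linked event one overall maximum in the period of first onset would put a post-restart worsening into the original-regimen table.

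The cost is one SAP paragraph, one derivation in the AE dataset, and some record-linking review before database lock. No new data collection is needed.
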